1. LIST OF ABBREVIATIONS

CCS	Canadian Cardiovascular Society
CFR	Coronary flow reserve
CTO	Chronic total occlusion
FFR	Fractional flow reserve
IMR	Index of microcirculatory resistance
IVUS	Intravascular ultrasound
MACE	Major adverse cardiovascular events
NYHA	New York Heart Association
OCT	Optical coherence tomography
PCI	Percutaneous coronary intervention
Pd/Pa	Pressure-distal / pressure-aorta = ratio of mean resting distal coronary pressure to aortic pressure
POBA	Plain old balloon angioplasty
RFR	Resting full-cycle ratio
SSR	Suboptimal stent result
ST	Stent thrombosis
TLR	Target lesion revascularization
TVF	Target vessel failure

2. SUMMARY

Rationale:

Post-percutaneous coronary intervention (PCI) intra-coronary physiology emerges as a useful tool to assess acute stent results. After PCI of non-chronic total occlusions (CTOs), several previous studies suggested a relationship between low post-PCI fractional flow reserve (FFR) and future adverse cardiac events ^{1, 2}. Non-hyperemic pressure ratio is a new category of resting indices, such as resting full-cycle ratio (RFR), that is calculated by measuring a resting pressure gradient across a coronary lesion under resting conditions (i.e. without pharmacologic hyperemia, as opposed to FFR) to assess the hemodynamic significance of a stenosis ³. A non-hyperemic pressure ratio, such as RFR, is theoretically less subject to the factors influencing FFR after PCI of a CTO, such as total stent length or acutely smaller diameters of the newly reperfused CTO vessel. However, the usefulness of post-PCI RFR in these patients remains to be elucidated. The ULTRA-CTO study will primarily evaluate both the value of post-PCI RFR and post-PCI FFR for detecting suboptimal stent result (SSR) in the acute phase. The components of SSR are depicted in figure 1.

Hypothesis: The hypothesis is that the area under the curve (AUC) of post-PCI RFR is non-inferior to the AUC of post-PCI FFR in CTO patients with regard to prediction of suboptimal stent result (SSR).

Primary objective: To assess the predictive value of post-PCI RFR and FFR with regard to SSR in CTO patients.

Secondary objectives:

To assess:

- The predictive value with regard to SSR of the RFR and FFR gradient across the stented segment.
- The correlation between post-PCI physiology (RFR, FFR, CFR, IMR) and SSR with anginal complaints (SAQ score), cardiovascular events and clinical (CCS and NYHA) classification
- The impact on physician-decision making based on OCT and physiology findings.

Study design: Prospective, multicentre, non-randomised investigator-initiated trial with a non-inferiority design

Study population: All patients of 18 years and older who are accepted for and successfully treated by PCI CTO in whom physiology measurements and OCT recordings are possible.

Main study endpoint: The AUC of post-PCI RFR compared to the AUC of post-PCI FFR with regard to SSR.

Nature and extent of the burden and risks associated with participation, benefit and group relatedness: The anticipated benefit is improvement of our knowledge on how to optimize stent results in CTO PCI. Because the pressure wires and OCT camera that are used for the study-related measurements are commonly used interventional tools, this poses no study-related additional risk for participating patients. International guidelines recommend the use of intravascular imaging for PCI guidance, especially in complex cases leading to lower myocardial infarction, TVR and cardiac mortality. Pressure wires are clinically indicated to identify hemodynamic significant (remaining) lesions that needs to be revascularized. Due to study-related measurements the procedures will be moderately prolonged, most likely by approximately 15 minutes.

With minimal effort and risk, subjects included in this trial are able to contribute to research to that may improve the treatment of CTOs, which may have large impact on clinical practice and guidelines.

3. INTRODUCTION AND RATIONALE

Post-PCI intra-coronary physiology emerges as a useful tool to assess acute stent results. Several previous studies suggested a relationship between low post-PCI FFR and future adverse cardiac events ^{1, 2}, although an optimal cutoff value has not been reported. Non-hyperemic pressure ratio (NPR) is a new category of resting indices, such as resting full-cycle ratio (RFR), among others, that is calculated by measuring a resting pressure gradient across a coronary lesion under resting conditions (i.e., without pharmacologic hyperemia) to assess the hemodynamic significance of a stenosis ³. The use of RFR instead of hyperemic physiology omits the use of a vasodilator, allowing the physician to perform multiple physiology assessments in less time and improving patient experience. In addition, RFR is potentially useful in the assessment of tandem lesions with minimal interaction between individual coronary stenoses. Currently, no data are available regarding post-PCI RFR or other non-hyperemic pressure ratios with regard to clinical outcome and stent result.

In the FFR-Search registry ⁴, 50% of all patients had a suboptimal FFR (≤ 0.90) after PCI with good angiographic result. Complex lesion characteristics, use of multiple stents and smaller reference vessel diameter were associated with a suboptimal FFR. This may explain an even higher rate of suboptimal FFR in chronic total occlusion (CTO) patients despite satisfactory angiographic results (65%) in the FFR-Search registry, but CTO lesions were present in only 5% of the total patient cohort. Karamasis et al. ⁵ also showed that post-PCI FFR ≤ 0.90 was present in 69% and ≤ 0.80 in one-third of patient after successful CTO PCI (n=26). The high incidence of low post-intervention FFR might be present in this particular group of patients because of longer stented segments and suboptimal stent results, including stent underexpansion, strut malapposition, stent edge dissection/hematoma, in-stent tissue protrusion ^{6, 7}, or acutely smaller diameters of the newly reperfused CTO vessel.

Of note, studies including patients with an increased complexity (i.e., CTO or lesion length >28 mm) demonstrated a consistent benefit of intravascular ultrasound (IVUS)-guided PCI as compared with angiography only, mainly driven by a reduction of repeat revascularization for restenosis (MACE at 1 year: CTO-IVUS, 2.6% vs. 7.1%, P=0.035; IVUS-XPL, 2.9% vs. 5.8%, P=0.007) ^{8, 9}. Optical coherence tomography (OCT) guidance has been shown to be equivalent to IVUS guidance, but OCT might be more suitable to assess stent edge dissections and stent malapposition ¹⁰. Thus, OCT may play an important role in the CTO treatment algorithm, determining the need for adjunctive therapies as well as adequate stent sizing and optimizing stent placement.

This suggests that intra-coronary physiology and intra-coronary imaging might be very useful to guide post-procedure decision-making and optimization of CTO PCI. Karamasis et al.⁵ showed a significant 4 month recovery of post-PCI FFR in CTO (mean increase of 0.07 from 0.82 to 0.89). Previously, Werner et al. used a Doppler wire to measure coronary flow reserve immediately after CTO PCI and at 5 months follow-up. Their study showed an increase of coronary flow reserve (2.01±0.58 to 2.50±0.79) because of a decrease in the baseline (resting) average peak velocity¹¹. Although the investigators interpreted these findings as the result of the resolution of the microvascular dysfunction caused by the CTO, they did not confirm this with specific parameters that address microvascular resistance, such the index of microcirculatory resistance (IMR). Distal luminal enlargement of the recanalized CTO vessels might be the most important explanation for increasing FFR at follow-up, due to restoration of flow, shear stress, and vasomotor properties of the distal vessel after the CTO recanalization.

These combined findings question the reliability of FFR in the acute stage and suggest that FFR may not be the optimal physiologic tool to assess PCI-result in the acute stage. Also, further effort is warranted to understand the pathophysiological substrate of low post-PCI FFR in CTO patients. Coronary physiology measurements, including RFR, FFR, IMR and coronary flow reserve (CFR) and the addition of OCT, will lead to a better understanding of the functional and anatomical aspects of CTO PCI to guide further optimization of procedural results.

Although non-hyperemic pressure ratio, such as RFR, is theoretically less subject to the factors influencing FFR, the usefulness of post-PCI RFR remains to be elucidated.

The ULTRA-CTO study will primarily evaluate both the value of post-PCI RFR and post-PCI FFR for detecting suboptimal stent result (SSR) in the acute phase, and the stability of these measurements over time in a subset of patients with a staged procedure and repeated physiologic assessment.

4. OBJECTIVES

4.1 Primary objective

To assess the predictive value of post-PCI RFR and FFR with regard to SSR in CTO patients.

4.2 Secondary objectives

- To assess the predictive value with regard to SSR of the RFR and FFR gradient across the stented segment
- To evaluate the correlation between positive RFR (≤ 0.89) and positive FFR (≤ 0.80) with regard to SSR following angiographically satisfactory CTO PCI.
- To evaluate the correlation between post-PCI physiology (RFR, FFR, CFR, IMR) and SSR with anginal complaints (measured using the Seattle Angina Questionnaire [SAQ]¹²), cardiovascular events and other clinical classifications (CCS and NYHA)
- To assess the impact on physician-decision making based on OCT and physiology findings.

4.3 Exploratory objectives

- To assess the change in RFR, FFR and other physiologic parameters over time (subset of patients)

5. STUDY DESIGN

ULTRA-CTO is a prospective multicentre non-randomised investigator-initiated trial designed to enrol 200 subjects with an indication for PCI CTO.

After angiographically successful CTO PCI, intra-coronary physiologic assessment (RFR, FFR, CFR and IMR) and subsequent OCT of the CTO vessel will be performed. OCT may also be performed during a staged procedure when indicated (i.e. high contrast use, procedural duration, major dissection or other safety reasons according to the operator)..

[figure not shown]
When intra-coronary physiologic assessment or OCT is not possible at all, the patients will not be included in the study (6.1).

When the operator decides to optimize the stent result (post-dilation or additional stenting), based on the OCT and/or physiology, post-PCI RFR and FFR should be repeated.

For patients with a remaining intermediate stenosis (angiographically 30-90%) in a non-CTO vessel or major side branch of the CTO vessel with diameter ≥ 2 mm, clinically indicated FFR guided PCI will be planned within 4 ± 2 weeks. During this staged procedure, intra-coronary physiologic assessment (RFR, FFR, CFR and IMR) will be repeated in the CTO vessel for exploratory objectives (before additional PCI).

At 4 ± 2 weeks follow-up, the occurrence of cardiovascular events and clinical classification will be assessed for secondary objectives. See figure 2 for the study flow chart. A description of the primary and secondary endpoint(s) is included in paragraph 8.1.

Figure 2. Flowchart ULTRA-CTO

6. STUDY POPULATION

6.1 Inclusion criteria

In order to be eligible to participate in this trial, a subject must meet all of the following criteria:

- 1) Age 18 years and older.
- 2) Angiographically successful PCI CTO, which is considered acceptable and final by the operator, without any remaining lesion $\geq 30\%$ proximal to the stented segment.
- 3) Possibility to perform physiologic measurements and OCT of sufficient quality.
- 4) Patients willing and capable to provide written informed consent.

6.2 Exclusion criteria

A potential subject who meets any of the following criteria will be excluded from participation in this trial:

- 1) Contra-indication for adenosine.

6.3 Screen failures

Subjects will be screened in hospital based on the information available. Subjects fulfilling the eligibility criteria and who have provided informed consent (IC) will be enrolled in the trial. Subjects who do not meet these criteria will be considered screen failures. A minimal set of screen failure information is required to ensure transparent reporting of screen failure subjects and will be captured on trial electronic case report forms (eCRFs). No further clinical follow-up will be performed on these subjects.

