9.2 AEs and SAEs

9.2.1 Adverse events (AEs)

Adverse events (AEs) are defined as any undesirable experience occurring to a subject during the trial, whether or not considered related to coronary procedures. All AEs reported spontaneously by the subject or observed by the investigator or his staff will be recorded starting from enrolment onwards until follow-up or the staged procedure in a subset at 4 ± 2 weeks. Unchanged chronic conditions are not AEs and should not be recorded on the AE sheet.

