11.2 Recruitment and consent

Eligible patients meeting the inclusion criteria will be asked for IC by one of the cardiologists. Written IC will be obtained before the index PCI procedure. The information is intended to give each participant a thorough understanding of the purpose and the nature of the trial, the cooperation required, anticipated benefits, and potential hazards of the trial. The cardiologist also explains that the patient is completely free to refuse or to withdraw from the trial and that if he does so he receives standard treatment with the same degree of care.

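### The moment of enrolment is not fixed consistently, so a consented patient whose study measurement fails can fall outside adverse event recording and follow-up

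*Protocol*

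**What the plan says.** **Timing of consent and eligibility.** Section 11.2 states: "Written IC will be obtained before the index PCI procedure". Figure 3 marks both eligibility and consent in the pre-procedure column, and 8.3.1 (Baseline) has the operator told beforehand that the patient is participating.

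**Criteria.** Section 6.1 requires as criterion 2 "Angiographically successful PCI CTO, which is considered acceptable and final by the operator" and as criterion 3 "Possibility to perform physiologic measurements and OCT of sufficient quality".

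**Consequence of failure.** Section 5, describing what follows the PCI and referring back to 6.1, says: "When intra-coronary physiologic assessment or OCT is not possible at all, the patients will not be included in the study (6.1". Section 6.3 enrols those who meet the criteria and have consented. Of the others it says "Subjects who do not meet these criteria will be considered screen failures", and then "No further clinical follow-up will be performed on these subjects". It also says "A minimal set of screen failure information is required to ensure transparent reporting of screen failure subjects", but does not list the items.

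**Adverse events.** Under 9.2.1, AEs "will be recorded starting from enrolment onwards until follow-up or the staged procedure in a subset at 4 ± 2 weeks". Section 8.3.3 registers AEs and SAEs at discharge, and Figure 3 marks adverse events at the index procedure. Section 10.4 plans a descriptive safety analysis without naming the subjects it covers.

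**The concern.** Eligibility depends partly on whether the study's own measurements succeed. Those measurements use a pressure wire, an intravenous adenosine infusion and an OCT catheter in a newly reopened vessel. If something goes wrong and the recording cannot be obtained, the same event that ought to be reported may also make the patient ineligible. Ineligible patients have no stated AE recording and no trial follow-up.

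At stake is the completeness of the safety description in 10.4 and of the SAE reporting in 9.4. Both matter because the Summary and 11.3 assert that the measurements add no study-related risk. A safety record confined to patients whose measurements succeeded is poorly placed to test that assertion. A later statistical analysis plan could define a safety population, but it could not recover events that the protocol did not have collected.

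**Working it through.** The plan gives no figure for measurement failure or complications, so there is nothing to reproduce. The check consists of setting the sections side by side.

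1. Consent comes before the PCI (11.2), hence before any study measurement.
2. Criterion 2 cannot be known until the PCI is finished. The quality element of criterion 3 cannot be known until recordings are attempted. Neither fits an eligibility check completed at baseline (Figure 3).
3. Section 7.1.1 requires physiology before OCT. A patient whose OCT then proves impossible has therefore already had the wire and the adenosine. Exposure before criterion 3 is settled is built into the sequence.
4. Section 5 does not include such a patient, and 6.3 makes the patient a screen failure without follow-up.
5. Section 9.2.1 counts AEs from enrolment, and 6.3 enrols only those who meet all criteria.

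The protocol thus supports two readings:

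| | Enrolment at consent | Enrolment once all criteria are met |
|---|---|---|
| Support | 8.3.1 (Baseline), Figure 3, 8.5 | 5, 6.1, 6.3 |
| Does not fit | criteria 2 and 3; the screen-failure rule in 5 and 6.3 | eligibility at baseline in Figure 3 |
| Failed measurement after exposure | subject in the trial, AEs recorded | screen failure, no stated AE recording, no follow-up |

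For scale only, let f be the share of consented, successfully treated patients whose measurements fail. The protocol does not give f. To include 200 patients, 200/(1 − f) must be attempted, and the number left without follow-up is 200/(1 − f) − 200, rounded up:

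- f = 2%: 200/0.98 = 204.1, so 5 patients
- f = 5%: 200/0.95 = 210.5, so 11 patients
- f = 10%: 200/0.90 = 222.2, so 23 patients
- f = 20%: 200/0.80 = 250, so 50 patients

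If the event rate is p among included patients and q among those with failed measurements, the rate among all exposed patients is (1 − f)p + fq, while the trial reports p. Taking p = 1% (assumed):

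- f = 5%, q = 10%: 0.95 × 1% + 0.05 × 10% = 1.45%
- f = 5%, q = 30%: 0.95 × 1% + 0.05 × 30% = 2.45%
- f = 20%, q = 10%: 0.80 × 1% + 0.20 × 10% = 2.8%
- f = 20%, q = 30%: 0.80 × 1% + 0.20 × 30% = 6.8%
- f = 5%, q = 0: 0.95 × 1% = 0.95%, slightly below the reported 1%

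Under-counting of the rate therefore requires q to exceed p. That is plausible where a complication is what stops the measurement, but no figure in the protocol establishes it.

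**The case against.** The strongest reply is that participation begins at consent. Section 8.5 bars replacement of withdrawn subjects except where consent is withdrawn before the procedure starts, so it treats a consented patient as a trial subject by then. The baseline section and Figure 3 agree. The 5% dropout allowance in 6.4 would also fit enrolled subjects who yield no usable data, although 6.4 gives no reasons for dropout. On this view a failed measurement is a dropout and its AEs are recorded. This reply stands as a tenable reading. It does not settle the matter, because Sections 5 and 6.3 then have no consistent application to criteria 2 and 3.

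Sections 9.3 and 9.4 collect SAEs over the whole trial and state no enrolment limit. That helps, but neither section is extended to screen failures or lifts the rule in 6.3.

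A reader might infer four stronger things, which the documents do not support:

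- **That AEs during the measurements are lost even in patients who are later included.** Figure 3 marks adverse events at the index procedure, and 8.3.3 registers them at discharge.
- **That every abandoned measurement makes a screen failure.** Section 5 speaks of measurements that cannot be done at all, which is narrower than the quality condition in 6.1. The status of a partial recording is unclear.
- **That patients with deferred OCT stay unenrolled for weeks.** No section says so. Allowing deferral for dissection or other safety reasons (5, 7.1.2) is a way of keeping such patients in. What happens if the deferred OCT is never obtained is not stated.
- **That the safety result is shown to be biased.** No endpoint in 8.1 is a safety rate, 10.4 is descriptive, and the sponsor's power to halt in 9.1 is not tied to enrolled subjects. The screen-failure form may also hold safety items, since its content is not shown.

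**Conclusion.** The point holds as an inconsistency with a safety consequence. The protocol does not fix when enrolment occurs. Under its literal rules in 5, 6.1, 6.3 and 9.2.1, a consented patient already exposed to a study measurement that fails can fall outside AE and SAE recording and the 4 ± 2 week follow-up. The descriptive safety analysis may therefore under-count study-related events.

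The size cannot be stated. It depends on the failure rate and on how often a complication causes the failure, and the protocol gives neither. The figures of 5 to 50 unfollowed patients, and of 1.45% to 6.8% against a reported 1%, rest wholly on assumed inputs. They show scale and are not estimates. The conclusion also rests on the stricter reading of enrolment; if the sponsor meant enrolment at consent, the remedy is simply to say so and bring 5 and 6.3 into line. Patients harmed after adequate recordings stay in the data, and the primary AUC comparison is not affected.

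**What to change.** Reconcile Sections 5, 6.1, 6.3, 9.2.1 and Figure 3, and state when a subject is enrolled. Specifically:

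- **9.2.1:** start AE and SAE recording at signed consent or, at the latest, at the first study measurement.
- **6.3:** limit the rule of no further clinical follow-up to subjects in whom no study measurement was started.
- **10.4:** describe safety for all consented subjects in whom a study measurement was started, whether or not the recordings were usable.
- **6.1 and 5:** use criterion 3 only to define the set for the primary AUC comparison, and say how partial recordings and a deferred OCT that is never obtained are classed.
- **Figure 3:** show that the criteria depending on the PCI are confirmed after it.

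The recruitment target should still count subjects with usable measurements. Otherwise failures would draw on the 5% dropout allowance, which is 200 × 0.05 = 10 patients. With that kept, the primary set is unchanged. The cost is protocol wording and one contact at 4 ± 2 weeks for the few patients with failed measurements. No extra procedures are needed.

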6.4 Sample size calculation

This study is aimed at assessing a difference in the AUCs of paired data where each subject (with and without SSR) is subjected to FFR and RFR measurement post-PCI. This procedure compares two ROC curves for the paired sample case where in each subject has a known condition value (SSR) and test values from two diagnostic tests (RFR and FFR). The test values are paired because they are measured on the same subject.

Researchers wish to show that a new classification method works at least as well as the current method. The trial is powered for non-inferiority.

Based on previous studies the area under the curve of FFR in relation to SSR is assumed to be 0.90 and the incidence of SSR is assumed to be 40%^{6, 7, 13}.

Assuming an AUC of 0.90 for FFR, with a significance level α of 5%, and a non-inferiority limit margin 0.10 and an estimated prevalence of SSR of 40%, a total of 190 patients are needed to obtain a power of 80%. To account for a drop out of 5%, the sample size will be increased to 200 patients.

7. TREATMENT OF SUBJECTS

7.1 Overall treatment

Patients will be medically treated according to the international guidelines. Screening of eligible patients will be performed by the researchers. Eligible patients meeting the inclusion criteria will be asked for informed consent by one of the researchers. The PCI procedure, intra-coronary physiologic assessment and OCT will be performed according to local guidelines and common practice. The study-related measurements at index - and staged procedure are described below and more detailed in a designated Standard Operating Procedure (SOP).

